9.6. Physical Examination

Clinically significant new or worsened physical examination abnormalities following treatment will be recorded as AEs and will be reflected in the summary of AEs.

10. PHARMACOKINETIC ANALYSIS

The PK analysis plan and report will be done separately.

A horizontal bar chart with 12 categories on the x-axis and 12 bars on the y-axis. The bars are black and of varying lengths. The categories are: 1 (shortest), 2, 3, 4, 5, 6, 7, 8, 9, 10, 11, 12 (longest). The bars for categories 1, 2, 3, 4, 5, 6, 7, 8, 9, 10, 11, and 12 are all black. The bar for category 12 is the longest, followed by categories 5, 11, and 10.

Category	Value
1	1
2	2
3	3
4	4
5	5
6	6
7	7
8	8
9	9
10	10
11	11
12	12

13. SUBGROUP ANALYSIS

The primary efficacy endpoints may be summarized as descriptive statistics by subgroups in **Table 4** in the mITT analysis set.

Table 4: Subgroups Defined at Baseline

Subgroup	Values
Age group	<65 years, ≥65 years
Sex	Female, Male
Race	White, Non-white (American Indian or Alaska Native, Asian, Black or African American, Native Hawaiian or Other Pacific Islander, Other)

14. INTERIM ANALYSES

Unblinded efficacy data endpoint review and unblinded interim analyses may be performed for individual cohorts while enrollment is ongoing; one possible unblinded interim analysis for a given cohort may be conducted, for example, when approximately 12 subjects have been randomized in the cohort and treated for at least 8 weeks. The purpose of the interim analysis is to assess for potential early signals of efficacy to inform updates of the clinical development plan. The interim analysis will be performed by an unblinded independent biostatistician; unblinded results will be communicated to selected Sponsor members who are not involved with the conduct of the study. Investigators and subjects will remain blinded to treatment assignment until after database lock and completion of the clinical study report (CSR).

15. DATA HANDLING CONVENTIONS

15.1. General Conventions

Imputation rules for the missing AE onset date

For the partial date (missing day and/or month) of AE start date, the following imputation rules will be applied:

- If AE Start Date year is equal to the year of the first dose and the AE end date is not before (<) the first dose, then the day and month will be imputed with the day and month of the first study dose date. Note: Partial missing / missing AE End date is considered as ‘not before/on first dose’. Otherwise, the month and day is imputed as the first day of the year (01 Jan).
- If only day is missing, and if the year and month are equal to the first dose date and AE end date is not before (<) the first dose, the AE start date will be imputed as the first dose date. Note: Partial missing / missing AE End date is considered as ‘not before/on first dose’. Otherwise, the day will be imputed as “01”.

Imputation rules for the missing CM or MH onset date

For partially missing CM or MH dates (missing day and/or month), the following imputation rules will be applied:

- If CM or MH start date day and month are missing, the start date is imputed as the first day of the year (01 Jan) and impute the end date as the last day of the year (Dec 31).
 - If only day is missing, the start date is imputed as the first day of the month (01).

Impose the end date as the last day of the month (28, 30 or 31 depending on month). Consider leap year.

The imputed dates need to be capped by end of study dates, death dates, and cutoff dates when they are applicable.

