**7.5 Safety and Tolerability Assessments**

**7.5.1 Adverse Events**

The investigator is responsible for collecting all AEs that are observed or reported during the study from the time the subject signs the ICF through the EOS Visit (Week 18), regardless of their relationship to study drug or their clinical significance.

An adverse event (AE) is any untoward medical occurrence in a clinical investigation subject administered a pharmaceutical product, which does not necessarily have a causal relationship with this treatment. An AE can therefore be any unfavorable and/or unintended sign (including an abnormal laboratory finding), symptom or disease temporally associated with the use of a medicinal (investigational) product, whether or not related to the medicinal (investigational) product.

AEs also include: any worsening (i.e., any clinically significant change in frequency and/or intensity) of a pre-existing condition that is temporally associated with the use of the study drug and abnormal laboratory findings considered by the reporting investigator to be clinically significant.

A TEAE is defined as any event not present before exposure to study drug or any event already present that worsens in either intensity or frequency after exposure to study drug.

The condition of subjects will be monitored from time of signing the ICF through the EOS Visit (Week 18). In addition, subjects will be observed for any signs or symptoms and asked about their condition by open questioning, such as “How have you been feeling since you were last asked?”, at every study visit from the Screening Visit through the EOS Visit (Week 18).

All non-serious AEs, whether volunteered, elicited, or noted on the physical examination, and serious adverse events (SAEs) will be recorded from the Screening Visit (signing the ICF) through the EOS Visit (Week 18). The AE information collected during the period from the Screening Visit until study drug administration on Day 1 is intended only for establishing a baseline status for subjects and for recording any screening procedure-related AEs. The nature, time of onset, duration, and severity of all AEs, both serious and non-serious, will be documented, together with an Investigator’s opinion of the relationship to study drug administration.

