9.2. Adverse Events

Adverse events will be mapped to preferred term (PT) and system organ class (SOC) using the most up to date Medical Dictionary (MedDRA) version 21.1. Treatment emergent AEs (TEAEs) are defined as all AEs started since the first dose date in the treatment period or all AEs occurred in the follow-up period. Furthermore, if an AE cannot be determined as treatment-emergent due to incomplete/missing data, conservatively, it will be considered as treatment emergent and included in the summary tables.

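### For an AE start known only to the first-dose year, SAP 15.1 ignores a recorded end month before dosing, dates onset after the event's own end, and makes it a TEAE

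*SAP*

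**What the plan says.** SAP 15.1 has two bullets for partial AE start dates.

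- **First bullet.** It begins "If AE Start Date year is equal to the year of the first dose and the AE end date is not before" first dose, and continues "then the day and month will be imputed with the day and month of the first study dose date". If the condition fails, the start becomes 01 January of the start year. Because this bullet fills in both day and month, and the second covers a missing day alone, it governs starts with the month unknown.
- **Second bullet.** It begins "If only day is missing, and if the year and month are equal to the first dose date" and applies the same end-date test. If the condition fails, the day becomes 01.

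Both bullets carry the same note: "Partial missing / missing AE End date is considered as" not before first dose. The section closes with "The imputed dates need to be capped by end of study dates, death dates, and cutoff dates" where applicable. The AE's own end date is not among these caps.

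Under SAP 9.2, TEAEs "are defined as all AEs started since the first dose date in the treatment period", or occur in follow-up. The same section adds that "if an AE cannot be determined as treatment-emergent due to incomplete/missing data, conservatively, it will be considered as treatment emergent".

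Protocol 7.5.1 collects AEs from consent. It says that what is collected before Day 1 dosing "is intended only for establishing a baseline status for subjects" and for recording AEs caused by screening procedures. It defines a TEAE as an event absent before exposure, or one already present that worsens after it.

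**The concern.** The end-date test in the first bullet separates events that were over before dosing from events that may not have been. The note disables that test for every partial end date, including one whose recorded month settles the question. Three things follow.

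- The analysis data can hold an AE with a start later than any possible end.
- An event that was over before exposure enters the TEAE tables. It meets neither part of the protocol's TEAE definition, and the protocol gives screening-period AEs a baseline role only.
- Classification turns on a trivial loss of detail: if the end day is missing and the end month is kept, a non-TEAE becomes a TEAE.

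The conservative fallback in SAP 9.2 does not justify this, because it is for events whose status cannot be determined. An end month before the dosing month determines it.

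**Working it through.** The plan states no figure to reproduce here. The check applies the two bullets literally, followed by the SAP 9.2 definition.

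**Inputs.** The imputation rules, note and caps come from SAP 15.1, and the TEAE definition from SAP 9.2. Screening of 14 to 28 days comes from Protocol 4.1 and SAP 2.3. The planned arms of about 16 and 10 subjects come from Protocol 8.4 and SAP 3. The calendar dates are assumptions: first dose on 15 May 2019, then every possible dose day in 2019.

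**Step 1. Test records, first dose 15 May 2019.**

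| Recorded start | Recorded end | Bullet | Imputed onset | TEAE? | Onset after latest possible end? |
|---|---|---|---|---|---|
| 2019 only | April 2019, day unknown | 1 | 15 May 2019 | Yes | Yes (latest end 30 April) |
| 2019 only | 28 April 2019 | 1 | 01 Jan 2019 | No | No |
| 2019 only | May 2019, day unknown | 1 | 15 May 2019 | Yes | No |
| 2019 only | 2019 only | 1 | 15 May 2019 | Yes | No |
| April 2019, day unknown | April 2019, day unknown | 2 | 01 April 2019 | No | No |
| May 2019, day unknown | May 2019, day unknown | 2 | 15 May 2019 | Yes | No |

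Only the first row is contradictory. Its onset falls at least 15 days after the event ended (30 April to 15 May). The second row is the same event with the end day known, and it is classified the opposite way. None of the three caps in SAP 15.1 (end of study, death, cutoff) changes the first row.

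**Step 2. Scope.** The second bullet assigns the first-dose date only when the start month equals the dosing month. An event cannot end in a month before the one it starts in, so the second bullet yields no such case. Nor does one arise when the end month falls in the previous year, because the start year then differs from the first-dose year.

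**Step 3. When the calendar allows it.** The pattern needs an earlier month of the same year to end inside the screening window. In 2019, eleven month-ends (January to November) can do this:

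- 28-day screening: 11 × 28 = 308 of 365 dose days (84%).
- 14-day screening: 11 × 14 = 154 of 365 dose days (42%).

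On each of these days, a year-only start with an end known to that month gives an onset after the end. These are days on which the pattern is possible. They are not error rates.

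**Step 4. Largest effect of one occurrence on overall TEAE incidence.** 1/16 = 6.25%, or 6.3 points, in the KPL-716 arm; 1/10 = 10 points in the placebo arm.

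**Step 5. With the latest compatible end date used instead.**

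- April 2019 becomes 30 April, before 15 May, so onset is 01 January and the event is not a TEAE.
- May 2019 becomes 31 May, and 2019 alone becomes 31 December. Neither is before 15 May, so both stay TEAEs as now.

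**The case against.** The strongest reply is that the case is close to empty. A pre-dose AE must fall between consent and Day 1, at most 28 days, so its onset lies within about two calendar months. Sites must record time of onset (Protocol 7.5.1) and review AEs before the first dose (Protocol 4.1.2.1). The validation checks in Protocol 10.1 and 10.2 would probably query a record with an end month but no start month. All of this stands as an argument about frequency. None of it changes the rule, which acts on whatever partial dates remain.

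The second reply is that the rule leans toward inclusion and is the same in both arms. That also stands: it adds TEAEs and removes none. But SAP 9.2 reserves that caution for undetermined timing.

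Stronger readings that a reader might infer are not supported:

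- **That drug-related TEAE tables are contaminated.** Protocol 7.5.1 requires both related categories to follow drug administration in a reasonable temporal sequence. An event over before any dose does not fit, and imputing a date does not alter the investigator's causality rating.
- **That true on-treatment incidence is hidden.** It can be inflated, but no on-treatment event is lost.
- **That every partial end date is affected.** The note stands in both bullets, but the contradiction arises only in the first, and only when the recorded end month precedes the dosing month.
- **That each occurrence moves incidence by 6.3 or 10 points.** The overview in SAP 9.2.1 counts subjects with any TEAE, so a subject who already has one adds nothing. Within an SOC or PT, the count rises only if the subject has no other TEAE in it.

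**Conclusion.** The point holds as a narrow defect in a stated rule. When the start month and day are missing, the start year equals the first-dose year, and the recorded end month precedes the dosing month, SAP 15.1 produces an impossible onset and SAP 9.2 counts the event as a TEAE. No other passage repairs this.

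The consequence is minor. The documents give no count of such records, and they should be few. Each adds at most one subject to overall TEAE incidence: at most 6.3 points with 16 subjects or 10 points with 10, if the planned arms are filled and the subject has no other TEAE. Efficacy and power are untouched. This is a tidy-up worth making because it is nearly free, and it does not threaten the safety conclusions.

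**What to change.** In the first AE-onset bullet of SAP 15.1 only, replace the note with:

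> A completely missing end date is treated as not before first dose. For a partial end date, use the latest date compatible with the recorded month/year; if that is before first dose, the event is treated as ended before first dose and the Otherwise rule of this bullet applies (01 Jan).

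Leave the second bullet alone. It yields no such case, and its own fallback (day 01) would conflict with a 01 January clause. SAP 15.1 already uses the same logic for concomitant medication and medical history, where an end date missing only its day takes the last day of the month.

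The cost is one SAP note and about one line of code. The conservative default stays wherever the recorded parts of the end date leave the timing open.

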17. APPENDICES

17.1. Study Schema and Schedule of Assessment

Study Visits	Screening	Treatment Period										Follow-up Period				
		Week (W)	W-4 to W0	Baseline	W1	W2	W3	W4	W5	W6	W7	W8	W10	W12	W14	W16
Day (D)	D -28 to -1	D1	D8	D15	D22	D29	D36	D43	D50	D57	D71	D85	D99	D113	D127	
Study Procedures	Windows (D)	0	±1	±2	±2	±2	±2	±2	±2	±2	±2	±2	±2	±2	±2	±2
Informed consent	X															
Demographics	X															
Medical and surgical history	X	X														
Prior medications, therapies, procedures	X	X														
Eligibility Assessment	X	X														
Safety Assessments																
Physical examination ¹	X	X		X		X		X		X		X		X		X
Vital signs ³	X	X	X	X	X	X	X	X	X	X	X	X	X	X	X	X
Body weight, height, BMI ²	X	X									X					X
ECG (12-lead) ³	X	X										X				X
Adverse Events Monitoring	From the Screening Visit through EOS Visit (Week 18)															

Study Visits	Screening	Treatment Period										Follow-up Period				
		Baseline	W1	W2	W3	W4	W5	W6	W7	W8	W10	W12	W14	W16	W18 (EOS)	
Week (W)	W-4 to W0															
Day (D)	D -28 to -1	D1	D8	D15	D22	D29	D36	D43	D50	D57	D71	D85	D99	D113	D127	
Study Procedures	Windows (D)	0	±1	±2	±2	±2	±2	±2	±2	±2	±2	±2	±2	±2	±2	±2
Concomitant meds/therapies/procedures monitoring	From the Screening Visit through EOS Visit (Week 18)															
Subject Compliance assessment	From the Screening Visit through EOS Visit (Week 18)															
Laboratory Tests																
Clinical laboratory blood tests	X	X		X		X		X		X		X		X		X
Urinalysis	X	X				X				X		X		X		X
Pregnancy test ⁴	X	X								X						X
Serology (HIV, HBV, HCV)	X															
Urine Drug Screen ⁵	X															
Dosing																
Randomization		X														
Study drug administration ⁶		X	X	X	X	X	X	X	X							
Study drug accountability		X	X	X	X	X	X	X	X							
Efficacy Measures																
Daily NRS Tool for assessment of pruritus and sleep	Completed daily from the Screening Visit through EOS Visit (Week 18)															
Pruritus VAS	X	X	X	X	X	X	X	X	X	X	X	X	X	X	X	X
Sleep Loss VAS	X	X	X	X	X	X	X	X	X	X	X	X	X	X	X	X
5-D Itch Scale	X	X		X		X		X		X	X	X	X	X	X	X
UAS7	Completed daily from the Screening Visit through EOS Visit (Week 18)															

Study Visits	Screening	Treatment Period										Follow-up Period				
		W-4 to W0	Baseline	W1	W2	W3	W4	W5	W6	W7	W8	W10	W12	W14	W16	W18 (EOS)
Week (W)	D -28 to -1	D1	D8	D15	D22	D29	D36	D43	D50	D57	D71	D85	D99	D113	D127	
Study Procedures	Windows (D)	0	±1	±2	±2	±2	±2	±2	±2	±2	±2	±2	±2	±2	±2	±2
ItchyQoL	X	X				X				X		X		X	X	
DLQI	X	X				X				X		X		X	X	
███████████		█		█		█		█		█		█		█	█	
███████████		█								█						
PK		X	X	X	X	X	X	X	X	X	X	X	X	X	X	
███████████		█		█		█				█		█		█	█	

███████████ BMI=body mass index; DLQI=Dermatology Life Quality Index; ECG=electrocardiogram; HBV=hepatitis B virus; HCV=hepatitis C virus; HIV=human immunodeficiency virus; ItchyQoL=Itchy Quality of Life; ██████████ PK=pharmacokinetic; UAS7=Urticaria Activity Score/over 7 days; VAS=Visual Analog Scale; WI-NRS=Worst itch numeric rating scale.

¹ At the Screening Visit and prior to dosing on Day 1, Week 8 and Week 18, a full physical examination will be performed including head/neck/thyroid, eyes/ears/nose/throat (EENT), skin, lymph nodes, respiratory, cardiovascular, gastrointestinal, musculoskeletal, and neurological exams. Breast, anorectal, and genital examinations will be performed only if medically indicated. At all other designated visits, an abbreviated physical examination will be performed including skin, cardiovascular, respiratory, and abdominal exams and as indicated based on subject's symptoms. A physical examination may be performed at any time if medically indicated per the Investigator's medical judgment.

[figure not shown]
² Height will be measured, and BMI will be calculated only at the Screening Visit.

[figure not shown]
³ECG and vital signs will be performed prior to blood draws, drug injections ██████████ ECG at Day 1 will be performed if it has been more than 30 days since screening ECG. Vital signs will be measured every hour during the observation period on dosing days.

[figure not shown]
⁴Females of childbearing potential only. A serum beta-human chorionic gonadotropin (βhCG) pregnancy test is performed at the Screening Visit. A urine βhCG test is performed at all later time points. A serum βhCG test is performed if urine βhCG test is positive.

⁵Additional screening for drugs of abuse may be performed at the discretion of the Investigator and in consultation with the Sponsor at any time during the study.

[figure not shown]
⁶ On dosing days, all procedures will be performed prior to dosing.

[figure not shown]

[figure not shown]
[figure not shown]
[figure not shown]

17.8. Clinical Laboratory Tests

Urinalysis	Hematology	Chemistry
APPEARANCE	ABS.BASOPHIL COUNT	IGE
BACTERIA	ABS.EOSINOPHIL COUNT	ALBUMIN
BILIRUBIN	ABS.LYMPHOCYTE COUNT	ALKALINE PHOSPHATASE
BLOOD	ABS.MONOCYTE COUNT	ALT
CA OXALATE CRYSTALS	ABS.NEUTROPHIL COUNT	AST
COLOR	APTT	BICARBONATE
EPITHELIAL RENAL	ATYPICAL LYMPHS	BILIRUBIN, TOTAL
EPITHELIAL SQUAMOUS	BANDS	BUN
EPITHELIAL TRANSITIONAL	BASOPHILS	CALCIUM
GLUCOSE	BASOS	CHLORIDE
GRANULAR CAST	BIZARRE PLATELETS	CHOLESTEROL, TOTAL
HYALINE CAST	BLASTS	CREATININE
KETONE	CALC.ABS.BASOPHIL COUNT	GGT
LEUKOCYTE ESTERASE	CALC.ABS.EOSINOPHIL COUNT	GLUCOSE, RANDOM
NITRITE	CALC.ABS.LYMPHOCYTE COUNT	HDL-CHOLESTEROL
PH	CALC.ABS.MONOCYTE COUNT	LDH
PROTEIN	CALC.ABS.NEUTROPHIL COUNT	LDL-CHOLESTEROL
RBC CAST	DIFF COMMENT	POTASSIUM
RBCS	EOS	PROTEIN, TOTAL
SPECIFIC GRAVITY	EOSINOPHILS	SODIUM
TRI PHOSPHATE CRYSTALS	FIBRINOGEN	TRIGLYCERIDES
URIC ACID CRYSTALS	GIANT PLATELETS	URIC ACID
UROBILINogen	HCT	
WAXY CAST	HGB	
WBC CAST	HYPERSEG.NEUTROPHILS	Serology
WBCS	I.N.R.	HEP B SURFACE AB
YEAST	LYMPHOCYTES	HEP B SURFACE AG
APPEARANCE	LYMPHS	HEP. C ANTIBODY
BACTERIA	MCH	HEPATITIS B CORE AB
	MCHC	HIV-1&2 AB SCREEN
	MCV	
Urine Drug Screen		
AMPHETAMIINE	METAMYELOCYTES	Others
AMPHETAMINES	MONOCYTES	Hemoglobin A1c
COCAINE METAB CONF.	MONOS	FSH
COCAINE METABOLITES	MYELOCYTES	PREGNANCY, QUALITATIVE
METHADONE	NEUTROPHILS	
METHAMPHETAMINE	NUCLEATED RBCS	
OPIATES	PLATELET COUNT	
OXYCODONE	PLATELET ESTIMATE	
PHENCYCLIDINE	PROMYELOCYTES	
	PROTIME	
	RBC	

RDW
REACTIVE LYMPHS
SEGS
SMUDGE CELLS
TOXIC GRANULATION
UNCLASSIFIED
WBC

17.9. Statistical Methods and SAS Codes

- **Analysis of Covariance (ANCOVA)**

The primary and secondary endpoints of change and percent change from baseline value by week will be analyzed using ANCOVA. The ANCOVA model includes factors of treatment, sex, and baseline value as a covariate. The following is an example of the SAS codes used to perform the analysis.

```
*****
```

* SAS Codes: *ANCOVA model*

* Variables in the model:

* chg = change from baseline in

* trt = treatment group code

* base = baseline value

* week = visit

```
*****;
```

```
proc mixed data=eff;  
  by week;  
  class trt;  
  model chg = trt base;  
  lsmeans trt /pdiff cl;  
run;
```

- **Fisher's Exact Test**

```
*****
```

* SAS Codes: Fisher's Exact Test

* Variables in the model:

* resp = response variable (Y/N or 1/0)

* trt = treatment group code

* week = visit number

```
*****;
```

```
proc freq data=dset order=data;  
  by week;
```

```
table trt*resp / alpha=0.05;  
exact relrisk fisher;  
output out=outname exact;  
run;
```

[REDACTED]

[REDACTED]

[REDACTED]

[REDACTED]

[REDACTED]

Signature Page for RIM-CLIN-001234 v1.0

Approval	[name] Legal 01-Oct-2021 12:48:07 GMT+0000
----------	---

Signature Page for RIM-CLIN-001234 v1.0
